6.8 Study Drugs

The specific information about Study Drugs will be described in the Study Drugs Handling Manual.

6.8.1 Test Drug : Counterpain® PXM

- Active Ingredients : Piroxicam plus Counterirritant (Methyl Salicylate, Eugenol and Menthol)
- Dose :
Adults : Refer to product's leaflet as follow: no occlusive dress should be employed. Apply gel to the affected area three times daily leaving no residual material on the skin. 1 gram of gel (~ 3 cm) applied to the affected area.

The affected areas are:

- The arms: hand, wrist, elbow, shoulder sinistra or dextra
- The legs: feet, ankle, knee sinistra or dextra
- Upper back or Lower back

3 times daily means:

- application one time in morning (06.00 – 11.00),
- one time in afternoon (11.01 – 17.00),
- one time in evening (17.01 – 23.00).

Application of gel will use dosing cards that provided in this clinical study.

- Method of administration: external use only.
- Every visit, participants will get 2 tubes and in total are 6 tubes for 6 ± 1 days application.

Justification:

The dosage for use refers to the Counterpain® PXM leaflet which has been approved by BPOM RI.

Refer to Counterpain® PXM data that 1 gram equal to 3 cm.

Counterpain PXM dalam gram	Setara dengan ukuran (cm)	Setara dengan assay Piroxicam (mg)	Kandungan zat Counterirritant didalamnya		
			Methyl Salicylate	Menthol	Eugenol
1 gram Counterpain PXM	3 cm	Mengandung Piroxicam 4.7 - 5.1 mg	Methyl Salicylate 97.2 - 119.17 mg	Menthol 48.5 - 55.9 mg	Eugenol 12.5 - 14.7 mg

1. 1 GRAM

[figure not shown]

Foto ukuran dalam cm yang setara dengan 1 gram Counterpain PXM

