6.8.2 Comparator Drug : Hotin® DCL

- Active Ingredients : Diclofenac Diethylamine 11.6 mg (Diclofenac Sodium 10 mg)
- Dose : Refer to the product's leaflet : no occlusive dress should be employed. Apply the required amount of cream on the affected area three times a day and rub gently. The amount of cream needed depends on the extent of the painful area. The affected area are :

- In the arms: hand, wrist, elbow, shoulder sinistra or dextra
- In the legs: feet, ankle, knee sinistra or dextra
- Upper back or Lower back

3 times daily means :

- application one time in morning (06.00 – 11.00),
- one time in afternoon (11.01 – 17.00),
- one time in evening (17.01 – 23.00).

Application of gel will use dosing card that provided in this clinical study.

- Method of administration: external use only.
- Every visit, participants will get 2 tubes and in total are 6 tubes for 6 ± 1 days application

Justification:

The dosage for use refers to the HOTIN DCL® leaflet which has been approved by BPOM RI

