6.8.3 Comparator Drug : Pirofel® gel

- Active Ingredients : Piroxicam 0.5%
- Dose :

Adults : Refer to product's leaflet as follow : no occlusive dress should be employed. Apply gel to the affected area three times daily leaving no residual material on the skin. 1 gram of gel applied to the affected area.

The affected area are :

- In the arms: hand, wrist, elbow, shoulder sinistra or dextra
- In the legs: feet, ankle, knee sinistra or dextra
- Upper back or Lower back

3 times daily means :

- application one time in morning (06.00 – 11.00),

- one time in afternoon (11.01 – 17.00),
- one time in evening (17.01 – 23.00).

Application of gel will use dosing card that provided in this clinical study.

- Method of administration: external use only.
- Every visit, participants will get 2 tubes and in total are 6 tubes for 6 ± 1 days application.

Justification:

The dosage for use refers to the Pirofel® gel leaflet which has been approved by BPOM RI.

Dosing Card

KARTU DOSIS

Aplikasikan obat topikal menggunakan kartu dosis ini langsung ke area yang nyeri.

1 gram setara dengan 3 cm

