6.13 Adherence of study drug

The dose of study drugs used during treatment period is checked based on the diary. If AE is occurred to the subject, Investigator can reduce or stop the dose of study drugs.

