- 9) Each participant will be given a pouch containing 2 tubes of investigational products, 3 dosing cards, 4 strips of rescue medications, a participant diary, a study coordinator business card and a PI or Sub-I business card.

The study's flow in Day 1 - Day 3 (\pm 1 day)

- 1) Participants will continue topical medication sessions at home. The Study Coordinator will assist with daily reminders for topical medication administration and diary completion. Participants will be asked to return to the study site on day 4 \pm 1 day with carrying the left over tubes and rescue medications, dosing cards, diary and put inside the pouch.
- 2) The participant will do the re-registration to registration officer and send back the pouch that will be given to the Fisiotherapist.
- 3) The examinations will remains same as Day 0 from poin 2 until 5.
- 4) The physiotherapist will provide information related to how to apply topical drugs to participants and applied the dose of the investigational product in the therapy room.
- 5) The administration of therapeutic drugs according to the randomization list by a physiotherapist. The physiotherapist will provide information related to how to apply topical drugs to participants and provide the dose of the investigational product in the therapy room.
 - o Form 7: Pemberian aplikasi obat topikal by Physiotherapist

- Form 8: Sensasi Termal by Participant

- 6) Each participant will be given a pouch containing 2 tubes of investigational products, 3 dosing cards, 4 strips of rescue medications, a participant diary, a study coordinator business card and a PI or Sub-I business card.
- 7) Participants will continue topical medication sessions at home. The Study Coordinator will assist with daily reminders for topical medication administration and diary completion. Participants will be asked to return to the study site on day 8 ± 1 with carrying the left over tubes and rescue medications, dosing cards, diary and put inside the pouch.

The study's flow in Day 5 - Day 6 (± 1 day)

- 1) Participants will continue topical medication sessions at home. The Study Coordinator will assist with daily reminders for topical medication administration and diary completion. Participants will be asked to return to the study site on day 6 ± 1 day with carrying the left over tubes and rescue medications, dosing cards, diary and put inside the pouch.

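### The dosing card's 1 gram = 3 cm is documented only for the test product but used in all three arms; for the diclofenac product it also conflicts with the dose text

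*Protocol*

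**What the plan says.** Protocol section 6.8.1 gives the test product's dose as "1 gram of gel (~ 3 cm) applied to the affected area", three times daily, and supports the length with "Refer to Counterpain® PXM data that 1 gram equal to 3 cm". The accompanying table covers that product alone and lists its piroxicam content per gram ("Mengandung Piroxicam 4.7 - 5.1 mg"). The photo caption also names only that product: "Foto ukuran dalam cm yang setara dengan 1 gram Counterpain PXM".

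The two comparator sections differ from this and from each other:

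- Section 6.8.3 (Pirofel, piroxicam 0.5%) states 1 gram per application and gives no strip length.
- Section 6.8.2 (Hotin DCL, diclofenac) states neither grams nor length. It lets the amount vary with the size of the painful area.

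Both comparator sections nevertheless dose by the card, in the same sentence: "Application of gel will use dosing card that provided in this clinical study". Section 6.8.1 says the same of the test product. The only card shown is printed at the end of section 6.8.3. It refers to topical medicine in general and reads "1 gram setara dengan 3 cm".

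On checking the amount used, section 6.13 says "The dose of study drugs used during treatment period is checked based on the diary". Under section 7.7.2, participants return to the site "carrying the left over tubes and rescue medications, dosing cards, diary", but no step weighs the tubes.

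**The concern.** A strip length measures weight only for the product and tube opening on which it was calibrated. The protocol shows a calibration for one product and prints the result on a card that names none. A Pirofel participant who dispenses exactly 3 cm each time follows the card perfectly, yet may not receive the 1 gram stated in section 6.8.3. Any such difference would affect the whole arm, so neither randomisation nor a larger sample would remove it.

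The objective in section 4 is equivalence of efficacy and safety, tested pairwise in section 7.4.2 against a margin of ±1.0. Pirofel against the test product is the most sensitive comparison. Both contain about 5 mg piroxicam per gram, so at equal grams the contrast reflects the counterirritants. If the grams differ, the amount of piroxicam is mixed into that contrast, for adverse events as well as pain.

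The diary would not expose this, because nothing in the protocol links it to a weight. The Per Protocol Set, which is the primary efficacy set, removes poor compliers (section 7.4.1), but a participant who always applied 3 cm would count as compliant whatever the strip weighed.

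**Working it through.** **Passages side by side**

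| Product | Amount stated in its section | Length-to-weight data shown | Card used |
|---|---|---|---|
| Test product (6.8.1) | 1 g, about 3 cm | Yes: table and photo | Yes |
| Hotin DCL (6.8.2) | No gram amount; varies with painful area | None | Yes |
| Pirofel (6.8.3) | 1 g, no length | None | Yes |

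**Can the conversion be reproduced?** No. The protocol gives no nozzle width or density for any product. What follows shows only how sensitive strip weight is to those two quantities.

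**Inputs.** From the protocol: 1 g = 3 cm; piroxicam 4.7 to 5.1 mg per gram of test product; Pirofel 0.5%, which is 5 mg per gram; three applications a day. Assumed: density ρ = 1 g/mL (range 0.90 to 1.05), a round strand, and the strand-width ratios below.

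**Step 1: strand width implied by the card.**
Mass = ρ × π × (d/2)² × length, so d = √(4 × 1 / (π × ρ × 3)).

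- ρ = 1.00: d = √0.424 = 0.651 cm, about 6.5 mm.
- ρ = 0.90: about 6.9 mm.
- ρ = 1.05: about 6.4 mm.

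**Step 2: weight of 3 cm from a different strand.** At equal density, the weight changes with the square of the width ratio r, so mass = 1 g × r².

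| Width relative to 6.5 mm | Weight of 3 cm | Piroxicam per day at 0.5% (mass × 5 mg/g × 3) |
|---|---|---|
| 20% narrower | 0.64 g | 9.6 mg |
| 10% narrower | 0.81 g | 12.2 mg |
| Equal | 1.00 g | 15.0 mg |
| 10% wider | 1.21 g | 18.2 mg |
| 20% wider | 1.44 g | 21.6 mg |

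**Step 3: comparison with the test arm.** At 1 g three times daily, the table in section 6.8.1 gives 4.7 × 3 = 14.1 to 5.1 × 3 = 15.3 mg piroxicam a day. Relative to 5 mg per gram, that content range runs from 4.7/5 = 0.94 to 5.1/5 = 1.02. A 10% difference in strand width alone would give 0.81 or 1.21, which is outside it.

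No corresponding calculation is possible for Hotin DCL, because its section states no gram amount to compare with the card.

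**The case against.** The strongest reply is that the protocol is not the only source. Section 6.8 refers specific drug information to a Study Drugs Handling Manual, and the dosing sections rest on the product leaflets. None of these is at hand, and comparator strip weights could be in the manual. That stands: the protocol shows no comparator calibration, but a reader may not infer that none was made. If the data exist, citing them settles the Pirofel point.

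Second, the widths in the table are assumptions. The protocol gives no nozzle dimensions, and the comparator strands could be close to 6.5 mm, in which case there is no error. That also stands. The wording of section 6.8.2 does not help decide: it calls the diclofenac product a cream in one place and a gel in another, which says nothing reliable about strand width.

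Third, section 6.8.1 presents 3 cm as approximate, and a single card protects participant blinding. Both are fair. However, approximation by individual participants is largely random, whereas a wrong conversion would shift a whole arm. Blinding is a reason to keep one card if the measured lengths agree, not a reason to leave them unmeasured.

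Two stronger readings are tempting and not supported. One is that both comparator arms depart from a stated 1 gram; section 6.8.2 states no gram amount. The other is that the comparators are under-dosed in favour of the test product. No direction is shown, and in a two-sided equivalence test a weakened comparator could equally push the difference outside ±1.0 and make equivalence fail.

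**Conclusion.** The point holds in limited form. The protocol documents 1 gram = 3 cm for the test product only and applies it, through a card that names no product, in all three arms.

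For Pirofel, a systematic departure from the stated 1 gram is possible, nothing in the protocol excludes it, and the diary check would not detect it. As an indication of sensitivity, a strand 10% narrower or wider than the implied 6.5 mm gives about 0.81 g or 1.21 g per application. This rests on an assumed density of 1 g/mL, a round strand and assumed widths; the actual size and direction are unknown.

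For Hotin DCL the defect needs no assumption: an amount that varies with the painful area and a card fixed at 1 g / 3 cm cannot both describe the dosing, and these passages must be reconciled.

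The sample size calculation is unaffected. This is an inexpensive safeguard for the equivalence comparison, not a demonstrated dosing error.

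**What to change.** 1. Before first dispensing, weigh replicate 3 cm strips of each of the three products at the sponsor plant that already relabels the tubes (section 6.12). If the Handling Manual already holds comparator data, cite them instead.
2. State the measured conversion for each product in sections 6.8.1, 6.8.2 and 6.8.3.
3. Keep a single card if the conversions agree. Only if they differ materially, make each card agree with the amount its own section states.
4. The sponsor should reconcile the area-dependent amount in section 6.8.2 with the fixed card. Which of the two applies is for the sponsor to decide; until then, step 3 cannot be carried out for that product.
5. Optional: weigh tubes at dispensing and return, and report grams used by arm descriptively. The point does not depend on this, and it need not become a criterion for the Per Protocol Set.

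**Cost.** A small bench check on a few tubes and short additions to three sections. The one real downside is that cards of different lengths could hint at allocation, so they would have to be packed with the coded tubes in a way that adds no cue. Optional weighing adds an entry at dispensing and another for tubes that already come back.

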6.8.2 Comparator Drug : Hotin® DCL

- Active Ingredients : Diclofenac Diethylamine 11.6 mg (Diclofenac Sodium 10 mg)
- Dose : Refer to the product's leaflet : no occlusive dress should be employed. Apply the required amount of cream on the affected area three times a day and rub gently. The amount of cream needed depends on the extent of the painful area. The affected area are :

- In the arms: hand, wrist, elbow, shoulder sinistra or dextra
- In the legs: feet, ankle, knee sinistra or dextra
- Upper back or Lower back

3 times daily means :

- application one time in morning (06.00 – 11.00),
- one time in afternoon (11.01 – 17.00),
- one time in evening (17.01 – 23.00).

Application of gel will use dosing card that provided in this clinical study.

- Method of administration: external use only.
- Every visit, participants will get 2 tubes and in total are 6 tubes for 6 ± 1 days application

Justification:

The dosage for use refers to the HOTIN DCL® leaflet which has been approved by BPOM RI

6.8.3 Comparator Drug : Pirofel® gel

- Active Ingredients : Piroxicam 0.5%
- Dose :

Adults : Refer to product's leaflet as follow : no occlusive dress should be employed. Apply gel to the affected area three times daily leaving no residual material on the skin. 1 gram of gel applied to the affected area.

The affected area are :

- In the arms: hand, wrist, elbow, shoulder sinistra or dextra
- In the legs: feet, ankle, knee sinistra or dextra
- Upper back or Lower back

3 times daily means :

- application one time in morning (06.00 – 11.00),

- one time in afternoon (11.01 – 17.00),
- one time in evening (17.01 – 23.00).

Application of gel will use dosing card that provided in this clinical study.

- Method of administration: external use only.
- Every visit, participants will get 2 tubes and in total are 6 tubes for 6 ± 1 days application.

Justification:

The dosage for use refers to the Pirofel® gel leaflet which has been approved by BPOM RI.

Dosing Card

KARTU DOSIS

Aplikasikan obat topikal menggunakan kartu dosis ini langsung ke area yang nyeri.

1 gram setara dengan 3 cm

6.9 Study Drugs Labelling

A label is needed for the study drug used.

Investigational products will be given to Participants in tube only, no individual box.

All Investigational Products tubes will be covered by white sticker, leaving only the tip of the tube containing the batch number and expiration date information. On top of the white sticker will be a study drug label that have specific code and number.

Below is the labelling process for investigational products :

The packaging label from investigational products will be covered by a white secured sticker. Only the bottom side (tail) which contains the batch number information is left open.

Clinical study label will be put on the top of white sticker.

PRODUK INVESTIGASIONAL NO. BATCH : 4M3101 TGL KADALUARSA : Dec 27 NO. REG : DTL1124403528A1 PENYIMPANAN : Simpan dibawah suhu 30° C <small>Dibuat oleh : PT. Taisho Pharmaceutical Indonesia, Tbk</small>	NO. OBAT : C001 NAMA SITE : Klinik Utama Eminence
PRODUK INVESTIGASIONAL NO. BATCH : 4M3101 TGL KADALUARSA : Dec 27 NO. REG : DTL1124403528A1 PENYIMPANAN : Simpan dibawah suhu 30° C <small>Dibuat oleh : PT. Taisho Pharmaceutical Indonesia, Tbk</small>	NO. OBAT : C199 NAMA SITE : St. Carolus Sports Clinic by Eminence

Final label on the tube

Every tube will be numbered with drug number sequentially, as detailed:

Test drug (Yellow sticker)	Comparator drug (Orange Sticker)	Comparator drug (Brown Sticker)
C001	H001	P001
C002	H002	P002
C003	H003	P003
etc. until the last of stock	etc. until the last of stock	etc. until the last of stock

- Initial “C” for study drug and 3 digits number
- Initial “H” for comparator drug and 3 digits number
- Initial “P” for comparator drug and 3 digits number

6.10 Rescue Medication

Rescue medication can be given to patient who have given informed consent. The rescue medication given is only if the subject can not bear the pain and to help reduce pain and per investigator advise. The rescue medication is a drug specifically provided for this study. The use of rescue medication will be recorded. The dosage of rescue medication will be determined by the Investigator.

- Active Ingredients : Paracetamol 600 mg
- Brand name : Sumagesic
- Dose : 1 tablets maximum 3 dose per 24 hours or refer to Investigator advise.
- Method of administration: Oral.

6.11 Storage Method

Please keep under 30° C, protect and avoid direct light. Kept until 1 month after the product opens.

6.12 Dispensing, Storage, Management, and Collection Procedures

The Study Drug Handling Manual will be provided and completed to ensure the study drugs are prepared, shipped, stored, dispensed, and returned to comply with regulations.

The Investigational Products will be relabelled in Sponsor Technical Operations Plant Site. After the Sponsor ensures the quality of the product, the study drug will be relabeled, which means that this drug is used explicitly for clinical studies.

The sponsor will deliver the study drug from the Technical Operations plant to each research site by courier, where it can monitor the temperature of the study drug delivery below 30°C.

The Study Coordinator from each research site will ensure the storage of study drugs.

During the study, the distribution of study drug participants will be prescribed by the Investigator based on randomization and dispensed to the participants by the Sports Therapist during the recovery program.

Use GraphPad QuickCalcs (<https://www.graphpad.com/quickcalcs/randomize1/>) to generate a random allocation list, ensuring equal numbers for each treatment group:

- Group A: Piroxicam + Counterirritant
- Group B: Piroxicam
- Group C: Diclofenac

Each eligible participant will be assigned a unique subject ID upon enrollment. The study coordinator will match the subject ID to a treatment group based on the pre-generated list. All tubes will be labeled with a sticker displaying only the randomization code to maintain blinding of both participants and investigators. The tube will then be dispensed to the participant according to the assigned code. Only the investigator will have access to the full randomization list.

At the end of the study period, all study drugs will be returned by the participants to each site. This return process will be assisted by each Study Coordinator. An then be sent to Technical Operations for destruction.

